1 INTRODUCTION

The following describes the Statistical Analysis Plan (SAP) for the analysis of data from HVTN 120 for Safety Monitoring Board (SMB) reports, the Final Study Report (FSR) for Safety, Protocol Team (PT) reports for immunogenicity data, and the FSR for Immunogenicity. As detailed in SCHARP SOP-0013, Revision 6 (effective date: May 1, 2018), this SAP is required prior to the first analysis and must be approved by the lead protocol statisticians. SMB reporting begins shortly after enrollment opens, and subsequent revisions are expected to describe analysis of immunogenicity data. The SAP will be reviewed prior to the first SMB report and before the final analysis with all major revisions of the plan archived.

1.1. General Design Considerations

Protocol Title

A phase 1/2a clinical trial to evaluate the safety and immunogenicity of ALVAC-HIV (vCP2438) and of MF59®- or AS01B-adjuvanted clade C Env protein, in healthy, HIV-uninfected adult participants

Study products and routes of administration

- **ALVAC-HIV (vCP2438)** expresses the gene products 96ZM651 *gp120* (clade C strain) linked to the sequences encoding the HIV-1 transmembrane anchor (TM) sequence of *gp41* (28 amino acids clade B LAI strain) and *gag* and *pro* (clade B LAI strain). It is formulated as a lyophilized vaccine for injection at a viral titer $\geq 1 \times 10^6$ cell culture infectious dose (CCID)₅₀ and $< 1 \times 10^8$ CCID₅₀ (nominal dose of 10^7 CCID₅₀) and is reconstituted with 1 mL of sterile sodium chloride solution (NaCl 0.4%), administered IM as a single 1 mL dose.
- **Protein/MF59:** Bivalent Subtype C gp120/MF59: clade C TV1.C gp120 Env and clade C 1086.C gp120 Env, each at a dose of 100 mcg, mixed with MF59 adjuvant, administered IM as a single 0.5 mL dose.
- **Protein/AS01_B:** Bivalent Subtype C gp120/AS01_B: clade C TV1.C gp120 Env and clade C 1086.C gp120 Env, each at a dose of 20 mcg or 100 mcg, mixed with AS01_B adjuvant, administered IM as a single 0.75 mL dose.
- **Placebo:** Sodium Chloride for Injection, 0.9%, administered IM.

Table 3-1 Schema

Group	N	Dose of each protein	Deltoid	Month 0 (Day 0)	Month 1 (Day 28)	Month 3 (Day 84)	Month 6 (Day 168)
1	50	100 mcg	Left	ALVAC-HIV	ALVAC-HIV	ALVAC-HIV	ALVAC-HIV
			Right	-	-	Protein/MF59 + Placebo*	Protein/MF59 + Placebo*
2	50	100 mcg	Left	ALVAC-HIV	ALVAC-HIV	ALVAC-HIV	ALVAC-HIV
			Right	-	-	Protein/AS01 _B + Placebo*	Protein/AS01 _B + Placebo*
3	50	20 mcg	Left	ALVAC-HIV	ALVAC-HIV	ALVAC-HIV	ALVAC-HIV
			Right	-	-	Protein/AS01 _B + Placebo*	Protein/AS01 _B + Placebo*
4	10	N/A	Left	Placebo	Placebo	Placebo	Placebo
			Right	-	-	Placebo + Placebo*	Placebo + Placebo*

* Two distinct placebo preparations for protein/adjuvant will be needed to maintain the blind since Protein/AS01_B and Protein/MF59 consist of different injection volumes.

Design

Multicenter, randomized, controlled, double-blind trial

Duration per participant

12 months of scheduled clinic visits

Estimated total study duration

18 months (includes enrollment and follow-up)

Investigational New Drug (IND) study sponsor

DAIDS, NIAID, NIH, DHHS (Bethesda, Maryland, USA)

Study Locations

Southern Africa and United States

Study Chair

[name]

1.2. Study Objectives and Endpoints

Primary objectives and endpoints

Primary objective 1

- To evaluate the safety and tolerability of ALVAC-HIV and bivalent gp120 protein/MF59 or bivalent gp120 protein/AS01_B.

Primary endpoints 1

- Severe local and systemic reactogenicity signs and symptoms (pain, tenderness, erythema, induration, fever, malaise/fatigue, myalgia, headache, nausea, vomiting, chills, arthralgia) up to 7 days after each vaccine dose
- AEs by body system, Medical Dictionary for Regulatory Activities (MedDRA) preferred term, severity, and assessed relationship to study products up to 30 days after each vaccine dose
- SAEs, AESIs, and new chronic conditions (requiring medical intervention for ≥ 30 days) throughout the study
- Laboratory measures: white blood cells (WBC), neutrophils, lymphocytes, hemoglobin, platelets, alanine aminotransferase (ALT), aspartate aminotransferase (AST), alkaline phosphate (ALP), and creatinine at baseline and following vaccinations
- AEs leading to early participant withdrawal or early discontinuation of study products administration throughout the study.

Primary objective 2

- To compare HIV-specific CD4+ T-cell response rates at the month 6.5 timepoint (2 weeks after the fourth vaccination) of ALVAC-HIV and bivalent gp120 protein/MF59 to each of the bivalent gp120 protein/AS01_B vaccine regimens.

Primary endpoint 2

- HIV-specific CD4+ T-cell response rates as assessed by flow cytometry.

Primary objective 3

- To compare HIV-specific Env-gp120 binding antibody response magnitudes at the month 12 timepoint (6 months after the fourth vaccination) of ALVAC-HIV and bivalent gp120 protein/MF59 to each of the bivalent gp120 protein/AS01_B vaccine regimens.

Primary endpoint 3

- HIV-specific Env-gp120 binding antibody response magnitude as assessed by multiplex assay.

Secondary objectives and endpoints

Secondary objective 1

- To further evaluate the systemic immune responses and the durability of immunogenicity of each vaccine regimen at the month 6.5 and month 12 timepoints.

Secondary endpoint 1

- HIV-specific total IgG binding antibody response breadth and magnitude as assessed by multiplex assay.
- Anti –V1/V2 scaffold IgG binding antibody responses as assessed by multiplex assay.
- HIV-specific CD4+ and CD8+ T-cell responses as assessed by flow cytometry.
- Additional immunogenicity assays may be performed on blood samples based on the HVTN Laboratory Assay Algorithm

Exploratory objectives

Exploratory objective 1

- To further evaluate immunogenicity of each vaccine regimen, additional immunogenicity assays may be performed on blood and optionally provided mucosal samples, including samples from other timepoints, based on the HVTN Laboratory Assay Algorithm.

Exploratory objective 2

- To assess whether the diversity of gut microbiome correlates with vaccine responses using optionally provided stool specimens.

Exploratory objective 3

- To conduct analyses related to furthering the understanding of HIV, immunology, vaccines, and clinical trial conduct.

1.3. Randomization

A participant's randomization assignment will be computer generated and provided to the HVTN CRS pharmacist through a Web-based randomization system. At each institution, the pharmacist with primary responsibility for dispensing study products is charged with maintaining security of the treatment assignments (except in emergency situations as specified in the HVTN MOP).

1.4. Blinding

Participants and site staff (except for site pharmacists) will be blinded as to participants' treatment group assignments. Study product assignments are accessible to those HVTN CRS

pharmacists, DAIDS protocol pharmacists and contract monitors, and SDMC staff who are required to know this information in order to ensure proper trial conduct. Any discussion of study product assignment between pharmacy staff and any other HVTN CRS staff is prohibited. The HVTN SMB members also are unblinded to treatment assignment in order to conduct review of trial safety.

When a participant leaves the trial prior to study completion, the participant will be told he or she must wait until all participants are unblinded to learn his or her treatment assignment.

In some cases, the CRS, PSRT, or study sponsor may believe unblinding of the site PI and participant would be appropriate to facilitate the clinical management of an AE or SAE. The HVTN Unblinding MOP specifies procedures for emergency unblinding, and for early unblinding for medical reasons.

1.5. Sample Size and Power

Safety

The goal of the safety evaluation for this study is to identify safety concerns associated with product administration. The ability of the study to detect SAEs can be expressed by the true event rate above which at least 1 SAE would likely be observed and the true event rate below which no events would likely be observed. Specifically, for each vaccine group of the study ($n=100$), there is a 90% chance of observing at least 1 event if the true rate of such an event is 2.3% or more; and there is a 90% chance of observing no events if the true rate is 0.1% or less.

Probabilities of observing 0, 1 or more, and 2 or more events among groups of size 100 are presented in Table 6-1 of the Protocol for a range of possible true adverse event rates. These calculations provide a more complete picture of the sensitivity of this study design to identify potential safety problems with a vaccine regimen.

An alternative way of describing the statistical properties of the study design is in terms of the 95% confidence interval (CI) for the true rate of an adverse event based on the observed data. Table 6-2 in the Protocol shows the 2-sided 95% CIs for the probability of an event based on a particular observed rate. Calculations are done using the score test method [1]. If none of the 100 participants receiving a vaccine regimen experience a safety event, the 95% 2-sided upper confidence bound for the true rate for such an event is 3.7%.

Immunogenicity

The primary immunogenicity evaluation is to compare Groups 2 and 3 (AS01B groups) separately to Group 1 (MF59 group) based on the following two criteria:

1. Establish superiority of the AS01B regimen in CD4+ T-cell response rate at month 6.5 for either TV1 or 1086; AND
2. Establish superiority of the AS01B regimen in magnitude of anti-gp120 antibody response at month 12 for 1086.

Power is calculated for each group comparison separately and assumes that:

1. The CD4+ T-cell response rate for the AS01B regimen is at least 20% higher for both antigens; AND,
2. The true geometric mean anti-gp120 binding antibody response is 1.5-fold higher for the AS01B regimen.

Power is based on data simulations using HVTN 100 CD4+ T-cell data from the month 6.5 visit (2 weeks after the fourth vaccination) and predicted anti-gp120 1086 antibody binding magnitude

at the month 12 visit. Simulated data sets were generated by sampling with replacement from the HVTN 100 data and power is reported as the percentage of the 10,000 simulated HVTN 120 trials that reject the composite null hypothesis defined by the primary immunogenicity evaluation (“Overall power”) and separately for the null hypotheses defined by the CD4+ T-cell and the anti-gp120 antibody criteria. CD4+ T-cell response calls were simulated for the MF59 group (Group 1) by dichotomizing the ICS IL2/IFN γ CD4+ T-cell response magnitude using a threshold defined by the observed response rates of 49% to the TV1 antigen and 40% to the 1086 antigen. For the AS01B comparator group (Group 2 or 3), CD4+ T-cell response calls were simulated based on threshold corresponding to response rates of 69% for TV1 and 60% for 1086 antigens. The rationale for this approach is to maintain the between antigen correlation and allow simulation of a higher response rate in the AS01B group. Predicted HVTN 100 Env-gp120 binding data at month 12 were used for the second primary immunogenicity criterion. Env-gp120 binding magnitudes in the MF59 group (Group 1) at month 12 were predicted using HVTN 100 month 6.5 data and assuming the same antibody decline between 6.5 and 12 months that was obtained from modelling the decline of the antibody response to the A244 gp120 antigen in RV144 [76]. AS01B (Group 2 or 3) IgG response magnitudes were simulated on a logit scale using a fold-change equivalent to a 1.5-fold change between group geometric means on the MFI scale. Specifically, the logit transformation of MFI is defined by $\text{logit}(\text{MFI}) = \log((\text{M-L})/\text{L}) - \log(\text{MFI}/(\text{M-MFI}))$ where $\text{M}=2^{15}$ and $\text{L}=100$, the upper and lower limits of detection of the binding assay multiplex assay (BAMA). The rationale for using the logit scale is to simulate MFI values within the range of the assay. Overall power, accounting for both primary immunogenicity criteria defined above, depends on inter-correlations between the CD4+ T-cell and anti-gp120 readouts. The correlation coefficient between month 6.5 TV1 and 1086 CD4+ Tcell magnitudes in HVTN 100 is high (0.86, Spearman rank correlation). Correlation coefficients between month 6.5 CD4+ T-cell magnitude (TV1 or 1086) and month 12 anti-gp120 1086 antibody magnitude are low (0.35 and 0.33, Spearman rank correlation). Although these correlations are difficult to interpret since they are based on predicted month 12 antibody responses, they are consistent with correlations between week 26 cellular and week 52 antibody responses from HVTN 096 and HVTN 205. Therefore, the results for overall power shown in Table 6-3 in the Protocol, are based on the correlation between month 6.5 CD4+ T-cell magnitude and predicted anti-gp120 1086 antibody magnitude. An alternative is to assume independence between the month 6.5 CD4+ T-cell responses and the month 12 anti-gp120 responses. Under this scenario the overall power is virtually the same (results not shown). Power calculations are based on 1-sided Fisher’s exact tests for the TV1 and 1086 CD4+ T-cell response rate comparisons and a 1-sided t-test comparing $\text{log}(\text{MFI})$ for the anti-gp120 responses comparison. Comparisons are based on an alpha level of 0.025.

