
2 ANALYSIS COHORT DEFINITIONS

Since enrollment is concurrent with receiving the first study vaccination, all participants will provide some safety data. However, for immunogenicity analyses, it is possible that data may be missing for various reasons, such as participants terminating from the study early, problems in shipping specimens, low cell viability of processed peripheral blood mononuclear cells (PBMCs), or high assay background. Immunogenicity data from 17 phase 1 and 2 phase 2a HVTN vaccine trials, which began enrolling after June 2005 (data as of September 2014), indicate that 15% is a reasonable estimate for the rate of missing data at month 6.5. For this reason, sample size calculations account for 15 enrolled participants on each of the vaccine groups having missing data for the primary immunogenicity endpoints.

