4.4.2 Missing data considerations

Based upon previous HVTN trials, missing 15% of immunogenicity results for a specific assay is common due to study participants terminating from the study early, problems in shipping specimens, or low cell viability of processed PBMCs. To achieve unbiased statistical estimation and inferences with standard methods applied in a complete-case manner (only including participants with observed data in the analysis), missing data need to be missing completely at random (MCAR). MCAR assumes that the probability of an observation being missing does not depend on any participant characteristics (observed or unobserved). When missing data are minimal (specifically, if no more than 20% of participants are missing values), then standard complete-case methods will be used, because violations of the MCAR assumption will have little impact on the estimates.

If a substantial amount of immunogenicity data are missing (at least 1 value missing from more than 20% of participants), then using the methods that require the MCAR assumption may give

misleading results. In this situation, analyses of the immunogenicity endpoints at a specific timepoint will be performed using parametric generalized linear models fit by maximum likelihood. These methods provide unbiased estimation and inferences under the parametric modeling assumptions and the assumption that the missing data are missing at random (MAR). MAR assumes that the probability of an observation being missing may depend upon the observed responses and upon observed covariates, but not upon any unobserved factors. Generalized linear models for response rates will use a binomial error distribution and for quantitative endpoints, a normal error distribution. For assessing repeated immunogenicity measurement, linear mixed effects models will be used. If the immunological outcomes are left- and/or right-censored, then the linear mixed effects models of Hughes [3] will be used, because they accommodate the censoring. In addition, secondary analyses of repeated immunogenicity measurements may be done using weighted GEE [4] methods, which are valid under MAR. All of the models described above will include as covariates all available baseline predictors of the missing outcomes.

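### The schema has 50 participants per vaccine group, but the safety precision figures and the missing-data allowance are those of 100 per group

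*SAP*

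**What the plan says.** **Schema.** Table 3-1 in SAP Section 1.1 gives 50 participants to each of the three vaccine groups: "1 50 100 mcg Left ALVAC-HIV", "2 50 100 mcg Left ALVAC-HIV" and "3 50 20 mcg Left ALVAC-HIV". Group 4 (placebo) has 10, so the total is 160.

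**Safety precision.** Section 1.5 sets n=100 for each vaccine group. On that basis it gives 2.3% as the true rate from which one or more events would be seen with 90% probability, and 0.1% as the rate up to which none would be seen with 90% probability. It then refers to a protocol table: "Probabilities of observing 0, 1 or more, and 2 or more events among groups of size 100". Finally, "If none of the 100 participants receiving a vaccine regimen experience a safety event, the 95% 2-sided upper confidence bound" is stated as 3.7%, using the score method.

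**Missing data.** Section 2 takes 15% as the expected missing rate and concludes that "sample size calculations account for 15 enrolled participants on each of the vaccine groups having missing data for the primary immunogenicity endpoints". Section 4.4.2 repeats the rate ("missing 15% of immunogenicity results for a specific assay is common") and keeps complete-case methods "if no more than 20% of participants are missing values".

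**The concern.** Fifty and 100 cannot both be the size of a vaccine group. This is not one mistyped digit: 100 appears three times in the Section 1.5 safety text and drives its figures, while 50 appears in three separate schema rows.

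Safety is the first primary objective, and Section 1.5 is where the SAP says what the trial can detect. If the schema is right, the stated sensitivity is too optimistic by roughly a factor of two, in the direction of false reassurance.

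The same conflict reaches the missing-data plan. A count of 15 per group, applied to groups of 50, would exceed the 20% limit in Section 4.4.2, although the 15% rate it is derived from would not. Section 2 also says the sample size calculations allow for this count, so the evaluable number behind the immunogenicity power is in doubt.

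**Working it through.** **Inputs.** Group size 50 (Table 3-1) or 100 (Section 1.5); score method and two-sided 95% level (Section 1.5); missing rate 15% and allowance 15 (Section 2); complete-case limit 20% (Section 4.4.2).

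**Reproducing the stated figures**

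| Quantity | Formula | SAP | n = 100 | n = 50 |
|---|---|---|---|---|
| True rate with 90% probability of one or more events | 1 − 0.1^(1/n) | 2.3% | 2.28% | 4.50% |
| True rate with 90% probability of no event | 1 − 0.9^(1/n) | 0.1% | 0.105% | 0.210% |
| Score upper bound for 0/n | 3.8415/(n + 3.8415) | 3.7% | 3.70% | 7.13% |
| Participants with missing data | 0.15 × n | 15 | 15 | 7.5 |

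All four stated figures match n=100. At that size Clopper-Pearson gives 3.62% and Agresti-Coull 4.44%, so the score bound is indeed the one used. Sizes of 85, 150 and 160 do not give the stated set either: the score bounds are 4.32%, 2.50% and 2.34%.

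**Reading the stated rates at n=50**
- True rate 2.3%: P(one or more events) = 1 − 0.977^50 = 0.688, not 0.90.
- True rate 0.1%: P(no event) = 0.999^50 = 0.951. The sentence stays true as an inequality, but 0.1% is no longer the 90% threshold.

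**Missing-data allowance**
- 15/100 = 15%, which matches the cited rate; 15/50 = 30%, which does not.
- At 50 per group, 3 × 15 = 45 vaccinees missing. That is 45/150 = 30% of vaccinees, or 45/160 = 28.1% of all participants even if no placebo recipient is missing. Both exceed 20%.
- At 100 per group the same count is 15% of vaccinees, below the limit.

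**Power, as an illustration only.** The SAP prints no power value, no simulation group size and no antibody SD. The evaluable number per group could be 100 − 15 = 85, 50 − 7 or 8 = 42 to 43, or 50 − 15 = 35.
- *CD4+ criterion (either antigen).* Section 1.5 inputs: 49% against 69% for TV1, 40% against 60% for 1086, Spearman correlation 0.86 between antigens, one-sided Fisher test at 0.025. Correlated binary data were simulated 400,000 times with latent correlation 2·sin(π × 0.86/6) = 0.870.
- *Antibody criterion.* Noncentral t for a difference of ln 1.5, one-sided 0.025, with an assumed SD on the ln scale of 0.5 to 1.1.
- *Overall.* Product of the two, assuming independence.

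| Evaluable per group | CD4+, either antigen | Antibody (SD 0.5 to 1.1) | Overall |
|---|---|---|---|
| 85 | 83% | 100% to 67% | 83% to 55% |
| 42 | 54% | 96% to 39% | 52% to 21% |
| 35 | 41% | 92% to 33% | 38% to 14% |

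At 43 evaluable, CD4+ power is 51% and overall power 49% to 20%; the dip from 42 reflects the discreteness of Fisher's test. The antibody column is a lognormal t-test approximation, not the SAP's resampling on a bounded logit scale.

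**The case against.** **Pooling.** Groups 2 and 3 both receive the AS01B-adjuvanted protein and together number 100. This does not rescue the text. Section 1.5 speaks of each vaccine group and of a single regimen, Group 1 has no partner to pool with, and the allowance of 15 applies to every vaccine group.

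**No analysis depends on the planned size.** This stands. Safety tables report observed counts and percentages, intervals use observed data, and the 20% missing-data rule and the 80% data-availability rule both work on actual participants. The prespecified analyses run unchanged at either size. The error lies in the design statements, not in an estimate.

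**The reader is not misled, because the 3.7% sentence is conditional on 100.** Partly fair: someone holding 0/50 can see that the sentence does not describe those data. But the SAP presents 100 as the actual size of each group, so the bound reads as a property of this trial.

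**The complete-case argument is the same error counted twice.** Also partly fair. The 20% rule is triggered by data actually missing, and 15% is below it at any size. The limit is exceeded only if the count of 15 is carried over to groups of 50. It shows that Sections 1.1, 2 and 4.4.2 do not fit together; it does not predict that the rule will be triggered.

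**The power figures prove nothing.** Correct as far as it goes. They rest on an assumed SD, and the SAP leaves power to a protocol table. They show only why the group size matters and do not establish that the trial is underpowered.

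**Conclusion.** The SAP contradicts itself on vaccine group size, and the contradiction must be fixed. The arithmetic in Section 1.5 is right for 100 and wrong for the 50 in the schema. If 50 is the true size, the zero-event upper bound is 7.1% instead of 3.7%, the threshold for a 90% chance of seeing an event is 4.5% instead of 2.3%, the no-event threshold is 0.2% instead of 0.1%, and the missing-data allowance is 7 to 8 per group instead of 15.

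These results need no assumption beyond the binomial model and the score method that the SAP names. The SAP alone does not show which size is intended. Any effect on immunogenicity power depends on the group size used in the simulation, which the SAP does not state.

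**What to change.** Settle the intended group size and make Table 3-1, Section 1.5 and Section 2 agree, checking them against the protocol tables that Section 1.5 cites.

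- **If 50 stands:** restate Section 1.5 with n=50 and the values 4.5%, 0.2% and 7.1%; refer to tables for groups of size 50; restate the Section 2 allowance as 7 to 8 participants per vaccine group, leaving about 42 evaluable.
- **If 100 is the true size:** correct Table 3-1. Section 1.5's safety figures and Section 2 can then stay.
- **Secondary, in either case:** state the evaluable number per group used in the power simulation. If it was 85 and 50 stands, re-run the simulation at about 42 per group and restate the power.

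The cost is SAP wording, plus at most one re-run of an existing simulation. No extra participants and no change to the planned analyses are needed.
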